7.3. Number of Subjects

A total of up to approximately 99 adult subjects are expected to enroll in this study.

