13.7. Sample Size Calculation

The sample size of this study was previously determined based on HbF responder rate, comparing the highest tolerated dose of IMR-687 to placebo, as the primary endpoint:

The sample size was determined assuming that the percentage of subjects who are HbF responders (i.e., have an HbF increase of $\geq 3\%$ from baseline) at Week 24 is 5% in the placebo arm and 35% in either of the IMR-687 arms, with a 20% dropout rate prior to Week 24. Based on these assumptions, 26 subjects/arm at Week 24 is sufficient to achieve 80% power to detect a difference between the highest tolerated IMR-687 dose and placebo in the HbF responders at Week 24 at a 2-sided significance level of 0.05.

Based on regulatory feedback, annualized rate of VOCs was elevated from a key secondary endpoint to the primary endpoint, with a corresponding change in statistical methodology:

Assuming that the actual data distribution is normal when the significance level (alpha) of the test is 0.05, the standard deviation is 2.7 in both groups, and there are no dropouts, there will be 88% power to detect a difference between the medians of 5.0 and 3.0 for the placebo and the IMR-687 highest tolerated dose groups, respectively (i.e., a 40% difference), using a 2-sided Wilcoxon rank-sum test.

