8.0 Study Design

This is a Phase 2b, randomized, double-blind, placebo-controlled, multicenter study of subjects aged 18 to 65 years with sickle cell disease (SCD; homozygous sickle hemoglobin [HbSS], sickle- β^0 [HbS β^0] thalassemia, or sickle- β^+ [HbS β^+] thalassemia) to evaluate the safety and efficacy of the phosphodiesterase type 9 inhibitor, IMR-687, administered once daily (QD) for 52 weeks. This study will enroll approximately 99 subjects with SCD. This study consists of a screening period (up to 4 weeks), a double-blind treatment period (52 weeks), and a safety follow-up period (4 weeks).

The study schematic is provided in [Figure 1](#) below, and the schedule of assessments is provided in [Appendix 3](#) of this document.

Subjects will receive either IMR-687 (lower dose or higher dose) or placebo in a blinded fashion. IMR-687 will be supplied as 100, 150, or 200 mg white tablets. Placebo and the different doses of IMR-687 are visually identical. Subjects will be advised to take 2 tablets orally, once daily (QD). Prior to the Protocol version 4.0, lower dose was defined as an exposure of ≥ 3.0 to ≤ 4.5 mg/kg, subjects in the lower dose group weighing <67 kg will be dispensed 100 mg tablets and those weighing ≥ 67 kg will be dispensed 150 mg tablets. Higher dose was defined as an exposure of >4.5 to ≤ 6.7 mg/kg, subjects in the higher dose group weighing <67 kg will be dispensed 150 mg tablets and those weighing ≥ 67 kg will be dispensed 200 mg tablets. In Protocol version 4.0 and later, lower dose was defined as an exposure of ≥ 3.4 to ≤ 5.0 mg/kg, subjects in the lower dose group weighing <60 kg will be dispensed 100 mg tablets and those weighing ≥ 60 kg will be dispensed 150 mg tablets. Higher dose was defined as an exposure of >5.0 to ≤ 6.7 mg/kg, subjects in the higher dose group weighing <60 kg will be dispensed 150 mg tablets and those weighing ≥ 60 kg will be dispensed 200 mg tablets.

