8.1 Sample Size and Power Considerations

8.1.1 Sample Size Determination

The sample size of this study was originally determined based on HbF responder rate as the primary endpoint:

Assuming a 5% HbF response rate for placebo, the study having approximately 31 placebo and 49 higher dose subjects would have > 85% power to detect a targeted difference of 30%, using a Chi-square test for comparison of proportions (with continuity-correction) and a two-sided alpha of 0.050. The assumed responder rate for placebo (5%) and highest tolerated dose subjects (>35%) includes the dropout subjects (regarded as are non-responders at Week 24).

Based on FDA feedback a new primary endpoint was adopted with a corresponding change in statistical methodology as specified in Section 8.1.2 below.

As of completion of this SAP, enrollment was completed in the ongoing study, with a total of 115 subjects randomized between August 2020 and August 2021. Out of the 115 subjects, the first 17 subjects were randomized in a 2:1 ratio to Lower Dose: Placebo, and the remaining 98 subjects proceeded with randomization in a 1:2:1 ratio for Lower Dose: Higher Dose: Placebo.

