8.1.2 Power Estimation

Annualized rate of VOCs was changed from a key secondary endpoint in Protocol 4.0/4.1 (April 2021) to the primary efficacy endpoint in this SAP and in Protocol Amendment 5.0/5.1 (February 2022). The power calculation below was based on the projection that there will be approximately 49 randomized subjects in higher dose, 35 subjects in lower dose and 31 subjects in placebo group.

Assuming that the actual data distribution is normal when the significance level (alpha) of the test is 0.050, the standard deviation is 2.7 in both groups, and there are no dropouts, there will be 88% power to detect a difference between the medians of 5.0 and 3.0 for the placebo and the IMR-687 highest tolerated dose groups, respectively (i.e., a 40% difference), using a two-sided Wilcoxon Rank-Sum test ([Table 1](#)). Assuming a 25% dropout rate, the power will be 78%.

Table 1 Power Estimation

| Scenarios | N for IMR-687 Highest Tolerated Dose | N for Placebo | Significance Level (two-sided alpha) | Standard Deviation | Difference | Power |
|------------------------|--------------------------------------|---------------|--------------------------------------|--------------------|------------|-------|
| No Dropout | 49 | 31 | 0.05 | 2.7 | 40% | 88% |
| With 25% Dropout Rate* | 37 | 24 | 0.05 | 2.7 | 40% | 78% |

* estimated based on Ataga et al.

The power calculation for the Annualized rate of VOCs was carried out in PASS Version 2020 v20.0.3. See [Appendix 7](#) for details.

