Appendix 7 Power Calculation for the Primary Endpoint (Annualized Rate of VOCs)

Wilcoxon 40% Effect Size - 0% Drop Out

Design

Solve For: Power

Test

Alternative Hypothesis: Two-Sided

Data Distribution: Normal

Alpha

Alpha: 0.05

Sample Size

Group Allocation: Enter N1 and N2 individually

N1: 31

N2: 49

Effect Size

Input Type: Means

Means

μ_1 : 5.034

μ_2 : 3

Standard Deviation

σ : 2.7

Mann-Whitney U or Wilcoxon Rank-Sum Tests

Numeric Results

$\delta = \mu_1 - \mu_2$

Hypotheses: H0: $\delta = 0$ vs. H1: $\delta \neq 0$

Data Distribution: Normal

| Power | N1 | N2 | N | μ_1 | μ_2 | δ | σ | Alpha |
|---------|----|----|----|---------|---------|----------|----------|-------|
| 0.88002 | 31 | 49 | 80 | 5.0 | 3.0 | 2.0 | 2.7 | 0.050 |

References

Al-Sunduqchi, Mahdi S. 1990. Determining the Appropriate Sample Size for Inferences Based on the Wilcoxon Statistics. Ph.D. dissertation under the direction of William C. Guenther, Dept. of Statistics, University of Wyoming, Laramie, Wyoming.

Julious, S. A. 2010. Sample Sizes for Clinical Trials. Chapman & Hall/CRC, Boca Raton, FL.

Zar, Jerrold H. 1984. Biostatistical Analysis (Second Edition). Prentice-Hall. Englewood Cliffs, New Jersey.

Report Definitions

Power is the probability of rejecting a false null hypothesis.

N1 and N2 are the number of items sampled from each population.

N = N1 + N2 is the total sample size.

μ_1 and μ_2 are the assumed population means.

$\delta = \mu_1 - \mu_2$ is the difference between population means at which power and sample size calculations are made.

σ is the assumed population standard deviation for each of the two groups.

Alpha is the probability of rejecting a true null hypothesis.

Summary Statements

Group sample sizes of 31 and 49 achieve 88.002% power to detect a difference of $\mu_1 - \mu_2 = 5.0 - 3.0 = 2.0$ using a two-sided Mann-Whitney U or Wilcoxon Rank-Sum test assuming that the actual data distribution is normal when the significance level (alpha) of the test is 0.050 and the standard deviation is 2.7 in both groups.

Wilcoxon 40% Effect Size - 25% Drop Out

Design

Solve For: Power

Test

Alternative Hypothesis: Two-Sided

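### The protocol's total of about 99 subjects does not give its stated 88% power; 88% was computed for 31 placebo and 49 higher-dose subjects out of 115, and the total was never updated.

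*Protocol*

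**What the plan says.** The protocol gives the planned total as approximately 99 in the synopsis, in 7.1 and in 7.3, where it reads "A total of up to approximately 99 adult subjects are expected to enroll in this study".

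Protocol 13.7, repeated in the synopsis, first describes an earlier sample size calculation for the HbF responder endpoint (26 subjects per arm at Week 24, 20% dropout). It then says the rate of vaso-occlusive crises became the primary endpoint and that "there will be 88% power to detect a difference between the medians of 5.0 and 3.0", for highest tolerated dose against placebo, "using a 2-sided Wilcoxon rank-sum test". The assumptions are that "the significance level (alpha) of the test is 0.05, the standard deviation is 2.7 in both groups, and there are no dropouts". No arm sizes accompany this second calculation.

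The SAP supplies them. Section 8.1.2 bases the power on "approximately 49 randomized subjects in higher dose, 35 subjects in lower dose and 31 subjects in placebo group", and Appendix 7 reports that "Group sample sizes of 31 and 49 achieve 88.002% power". Section 8.1.1 says enrolment was complete, "with a total of 115 subjects randomized between August 2020 and August 2021": the first 17 at 2:1 (lower dose to placebo) and the other 98 at 1:2:1 (lower, higher, placebo). SAP 8.0 nevertheless says "This study will enroll approximately 99 subjects with SCD".

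**The concern.** The protocol's only total is about 99 and its only power for the current primary endpoint is 88%. A reader will take them as belonging together and cannot test this, because the arm sizes are absent. The one arm size in Protocol 13.7, 26, belongs to the superseded HbF calculation.

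The dates make the mismatch harder to treat as plan against outcome. SAP 8.1.2 places the change of primary endpoint in the February 2022 amendment, and SAP 8.1.1 says randomisation ended in August 2021. The 88% therefore became the primary-endpoint power after 115 subjects were already in the trial, while the total stayed at 99.

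What is at stake is whether the size and power of the primary comparison can be reproduced from the protocol. The conduct and analysis of the trial are not affected.

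**Working it through.** **Inputs.** SD 2.7, two-sided alpha 0.05 and no dropout (Protocol 13.7). Difference 2.0 as stated in the text, or 5.034 − 3 = 2.034 as entered in the software (SAP Appendix 7). Allocation 2:1, then 1:2:1 (Protocol 7.1.2). First stage of 17 subjects (SAP 8.1.1 only).

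**Method.** Two-sample t-test power from the noncentral t distribution. Each arm is multiplied by 3/π, the Wilcoxon efficiency under normality, and rounded down to n1 and n2. The noncentrality is (difference/2.7)/√(1/n1 + 1/n2) on n1 + n2 − 2 degrees of freedom.

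**Step 1: reproduce the plan's figures.**
- 31 and 49: 31 × 3/π = 29.6, so 29; 49 × 3/π = 46.8, so 46. With difference 2.034 the noncentrality is 3.177, the critical value 1.993 and the power 0.88002, as in SAP Appendix 7.
- 24 and 37: these become 22 and 35, and power is 0.77644, again as in Appendix 7.
- With difference 2.0, 31 against 49 gives 0.869.

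**Step 2: check that 31/35/49 fits 115.** 17 at 2:1 gives 5.7 placebo and 11.3 lower dose. 98 at 1:2:1 gives 24.5 placebo, 24.5 lower and 49 higher. The sums are 30.2, 35.8 and 49, close to the SAP's 31, 35 and 49 (total 115).

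**Step 3: arm sizes at 99.** 99 − 17 = 82. Placebo is 5.7 + 82/4 = 26.2; higher dose is 82/2 = 41. The comparison is about 26 against 41.

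**Step 4: power at 99, same method.** 26 × 3/π = 24.8, so 24; 41 × 3/π = 39.2, so 39.

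| Difference | Noncentrality | Power |
|---|---|---|
| 2.0 | 2.855 | 0.802 |
| 2.034 | 2.904 | 0.815 |

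Without rounding down the figures are 0.811 and 0.824, and simulation of the Wilcoxon test gives the same.

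**Step 5: does the borrowed 17 matter?** At 99 subjects, using fractional arm sizes without rounding down:

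| First stage | Placebo / higher dose | Power (2.0 to 2.034) |
|---|---|---|
| 0 | 24.8 / 49.5 | 0.826-0.839 |
| 5 | 25.2 / 47.0 | 0.823-0.836 |
| 17 | 26.2 / 41.0 | 0.813-0.825 |
| 30 | 27.2 / 34.5 | 0.793-0.806 |

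The range is roughly 79-84%. At difference 2.034 and a 17-subject first stage, the smallest total reaching 88% is 115.

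**Step 6: replacements.** Protocol 8.6 allows up to 10, so 99 + 10 = 109, which does not account for 115.

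**The case against.** The best defence is that nothing was miscalculated. The 88% is exact for 31 against 49, the SAP discloses those sizes, the inputs and the 115, and the SAP states that it prevails where it differs from the protocol. That stands. A reader might infer that the 88% is an arithmetic error or that the trial is underpowered relative to its claim. The documents do not support either: for the 115 subjects actually randomised, 88% is the right no-dropout figure under the stated assumptions.

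It can also be said that the protocol never asserts in one sentence that 99 subjects give 88%, and that 99 looks like a remnant of the HbF calculation: 26/0.8 = 32.5, so 33 per arm, and 3 × 33 = 99. That derivation is plausible, but neither document states it. It explains the mismatch without removing it, because the current protocol offers no other total.

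SAP 8.0 can be read as repeating the plan while 8.1.1 reports the outcome, so calling the SAP self-contradictory would be too strong. It is a design paragraph left unrefreshed. It does mean that the precedence clause does not by itself tell the reader which total applies.

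Two further inferences fail. One is to cut 26 and 41 by 25% and set the result against the SAP's 78%. The SAP ties 78% to 37 and 24 from the 115, and no document ties it to 99. The other is that the protocol errs by omitting the 25%-dropout power and the 2.034 input. It states openly that no dropout is assumed, and the SAP gives both.

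**Conclusion.** The point holds as an inconsistency between a stated total and a stated power. At about 99 subjects the protocol's allocation gives about 80-82% power by the SAP's method, some 6.5 to 8 points below 88%. The 26-against-41 split rests on the SAP's 17-subject first stage, which the protocol does not contain; over first stages of 0 to 30 subjects the power stays at roughly 79-84%, so the conclusion does not depend on it. All figures assume normal data, SD 2.7, a difference of 2.0 to 2.034 and no dropout, as the plan does. No analysis, significance boundary or patient is affected. It should be corrected because the protocol as written does not support its own power statement.

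**What to change.** Wording only; no more patients and no change to the analysis.

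- In the protocol synopsis, 7.1, 7.3 and SAP 8.0, state 115 randomised (about 31 placebo, 35 lower dose, 49 higher dose). Alternatively, label 99 as the original plan for the HbF endpoint, once the sponsor confirms that origin.
- In Protocol 13.7 and its synopsis copy, put 49 higher dose and 31 placebo beside the 88%.
- If 99 is kept as the operative size, state about 81% instead of 88%.
- Optional: repeat in the protocol the SAP's 78% at 25% dropout, with its 37 and 24, and the 2.034 difference used in the software.

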8. SELECTION AND WITHDRAWAL OF SUBJECTS

8.1. Subject Inclusion Criteria

Each subject must meet all the following criteria to be enrolled in the study:

1. Male or female aged ≥ 18 to ≤ 65 years at the time of ICF signing.
2. Confirmed diagnosis of SCD (HbSS, HbS β^0 thalassemia, or HbS β^+ thalassemia) in the medical record; if not available, the diagnosis must be confirmed at the site's local laboratory instead.
3. Subjects must have had at least 2 and no more than 12 documented episodes of VOC in the past 12 months at the time of ICF signing and at randomization (Day 1).

For study eligibility, VOC is defined as a documented episode of an acute painful crisis (for which there was not an explanation other than VOC) that involved moderate to severe pain lasting for at least 2 hours and at least one of the following:

- Use of escalated analgesia (including healthcare professional-instructed use of an analgesic prescription)
- A hospital, emergency department, or clinic visit and/or healthcare telephone consultation at the time of occurrence
- Diagnosis of ACS (defined as an acute illness characterized by fever and/or respiratory symptoms, accompanied by a new pulmonary infiltrate on a chest X-ray), hepatic sequestration, splenic sequestration, or priapism (in males)

4. Hb of >5.5 and <10.5 g/dL; Hb values within 21 days post-transfusion will be excluded.
5. *This inclusion criterion has been removed.*
6. Subjects receiving HU must have received it continuously for at least 6 months prior to signing the ICF, and must have been on a stable dose for at least 3 months prior to signing the ICF, with no anticipated need for dose adjustments during the study including the screening period, in the opinion of the investigator.
7. Female subjects must not be pregnant or breastfeeding and be highly unlikely to become pregnant. Male subjects must be unlikely to impregnate a partner. Male or female subjects must meet at least one of the following criteria:
 - A female subject who is not of reproductive potential is eligible without requiring the use of contraception. A female subject who is not of reproductive potential is defined as one who: (1) has reached natural menopause (defined as 12 months of spontaneous amenorrhea without an alternative medical cause, and can be confirmed with serum follicle-stimulating hormone [FSH] levels in the postmenopausal range as determined by the central laboratory); (2) is 6 weeks postsurgical bilateral oophorectomy with or without hysterectomy; or (3) has undergone bilateral tubal ligation. Spontaneous amenorrhea does not include

cases for which there is an underlying disease that causes amenorrhea (e.g., anorexia nervosa).

- A female of reproductive potential must have 2 negative pregnancy tests as verified by the investigator prior to starting study therapy. She must agree to ongoing pregnancy testing during the course of the study, at the EOT visit, and at the EOS visit. This applies even if the subject practices true abstinence from heterosexual contact.
- A male subject who is not of reproductive potential is eligible without requiring the use of contraception. A male subject who is not of reproductive potential is defined as one who has undergone a successful vasectomy. A successful vasectomy is defined as (1) microscopic documentation of azoospermia or (2) a vasectomy more than 2 years ago with no resultant pregnancy despite sexual activity post-vasectomy.
- A male or female subject who is of reproductive potential agrees to remain truly abstinent or use (or have their partner use) acceptable methods of highly effective contraception starting from the time of consent through 3 months after the completion of study drug. True abstinence is defined as abstinence that is in line with the preferred and usual lifestyle of the subject. Periodic abstinence (e.g., calendar, ovulation, symptothermal, post-ovulation methods), declaration of abstinence for the duration of the study, and withdrawal are not acceptable methods of contraception. Acceptable methods of highly effective birth control are combined or progesterone-only hormonal contraception that is associated with inhibition of ovulation, intrauterine device, and intrauterine hormone-releasing system.

8. Be capable of giving informed consent and reading and signing the ICF after the nature of the study has been fully explained by the investigator or investigator designee.
9. Be willing and able to complete all study assessments and procedures and to communicate effectively with the investigator and site staff.

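### Inclusion criterion 7 links its bullets with an either/or, so read literally a woman of reproductive potential can satisfy the list by pregnancy testing without the contraception undertaking

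*Protocol*

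**What the plan says.** The numbered inclusion criteria in Protocol 8.1 are cumulative: "Each subject must meet all the following criteria to be enrolled in the study". Criterion 7 opens with a general rule, "Female subjects must not be pregnant or breastfeeding and be highly unlikely to become pregnant", and a parallel, softer rule for men. It then changes the logic for its bullets: "Male or female subjects must meet at least one of the following criteria". The synopsis has the same wording.

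The four bullets are:

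- Bullet 1: "A female subject who is not of reproductive potential is eligible without requiring the use of contraception".
- Bullet 2: "A female of reproductive potential must have 2 negative pregnancy tests as verified by the investigator prior to starting study therapy". She must also agree to continued testing, and the bullet adds: "This applies even if the subject practices true abstinence from heterosexual contact".
- Bullet 3: "A male subject who is not of reproductive potential is eligible without requiring the use of contraception".
- Bullet 4: "A male or female subject who is of reproductive potential agrees to remain truly abstinent or use (or have their partner use) acceptable methods". The undertaking runs from consent to 3 months after the last study drug. The bullet lists the accepted methods and rules out periodic abstinence and withdrawal.

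**The concern.** Bullets 2 and 4 both describe a woman of reproductive potential, and they ask for different things. Bullet 2 detects a pregnancy; bullet 4 is there to prevent one. With an either/or connector, meeting bullet 2 is enough, and the only specific contraception rule becomes optional for women to whom it is addressed.

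What is at stake is fetal exposure to an investigational drug. There is also a practical consequence. Monitors check adherence to the eligibility criteria (Protocol 14.2), but a woman with two negative tests and no contraception undertaking satisfies the list as written, so her missing undertaking need not appear as a deviation. Sample size, power, type I error and every planned analysis are untouched.

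**Working it through.** No figure in the plan depends on this, so the check is one of logic, followed by a search for any other rule that closes the gap and a check of timing.

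**Step 1: the list under each connector.**

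| Subject | Bullets that apply | Position | At least one | Every one that applies |
|---|---|---|---|---|
| Woman of reproductive potential | 2 and 4 | 2 met, 4 met | satisfied | satisfied |
| Same | 2 and 4 | 2 met, 4 not met | **satisfied** | **not satisfied** |
| Same | 2 and 4 | 2 not met, 4 met | satisfied | not satisfied |
| Woman not of reproductive potential | 1 | 1 met | satisfied | satisfied |
| Man of reproductive potential | 4 | 4 not met | not satisfied | not satisfied |
| Man not of reproductive potential | 3 | 3 met | satisfied | satisfied |

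The second row is the defect. The third row is its mirror image (testing becomes optional), but exclusion 5 and the visit schedule supply testing anyway. Each of the other three groups has only one applicable bullet, so the connector makes no difference. The problem is confined to women of reproductive potential.

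**Step 2: what was intended.** Bullets 1 and 3 release only subjects who are not of reproductive potential from contraception, which implies that everyone else needs it. Bullet 2 says that testing applies even to an abstinent woman, which makes sense only if testing is added to bullet 4. The intended rule is bullets 2 and 4 together.

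**Step 3: does another rule restore bullet 4?**

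- Criterion 7, opening sentence: binds every woman, but names no method and no duration.
- Exclusion 5 (Protocol 8.2), Table 1 note g and Protocol 11.3.6.5: pregnancy testing only.
- Protocol 12.1.2.5: recording, follow-up and withdrawal once a pregnancy has occurred.
- SAP: no contraception rule.

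None of these sets a method or the 3-month duration.

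**Step 4: can testing stand in for bullet 4?** The last scheduled test is at Week 56, 4 weeks (28 days) after Week 52 dosing. Using the SAP's month of 30.4375 days, 3 months is 3 × 30.4375 = 91.3 days. That leaves 91.3 − 28 = 63.3 days, about 9 weeks, of the bullet 4 period with no scheduled test.

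**Step 5: is it still live at the SAP date of 1 March 2022?** I assume that the first dose is on the day of randomization. SAP 8.0 dates the opening of the higher dose to 12 March 2021. From that date, 1 March 2022 is study day 355, short of Day 364, so nobody randomized in the 1:2:1 phase had reached the end of treatment. SAP 8.1.1 puts the last randomization in August 2021. If it was on 31 August, Day 364 is 29 August 2022, and 3 months later is 29 November 2022 (5 December 2022 with the 7-day visit allowance). Any drug taken in the open-label extension is not counted.

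**Step 6: would rewording the entry criterion reach anyone?** SAP 8.1.1 reports enrollment complete. Protocol 8.6 allows replacement only for withdrawals up to the Week 12 visit. For a subject randomized on 31 August 2021, Day 84 is 22 November 2021, or 27 November with the 5-day allowance. Both fall before the SAP date, so on these documents no further woman would be screened under a corrected criterion.

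**The case against.** The strongest reply is that the literal reading is strained. It would also make the mandatory wording inside bullet 2 optional and empty its remark about abstinence of meaning. A sensible investigator would read the bullets together. The opening sentence binds in any case, and a sexually active woman using no effective method could hardly meet it. Tests are scheduled at every on-site visit from baseline, and a pregnant subject is withdrawn. The consent form, which was not available, may already obtain the undertaking from every woman concerned.

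Most of this stands, and it limits the point. A reader might infer that a woman is eligible on testing alone, or that the sponsor waived contraception. The documents support neither: the opening sentence applies to her whatever she does under the list, and bullets 1 to 3 show the contrary intent.

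The reply does not remove the defect. Criterion 3 in the same section uses an at-least-one list as a genuine alternative, so sites have no textual signal to read criterion 7 differently. The opening sentence leaves both method and duration to judgment, including after dosing stops. Testing and withdrawal act only after exposure.

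**Conclusion.** The point holds as a wrong connector in a safety rule. Read literally, criterion 7 lets a woman of reproductive potential satisfy the list through bullet 2, and bullet 4, the only text in the protocol or SAP that gives contraceptive methods and the 3-month duration, is not mandatory for her. The rule for men works as written.

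Its size cannot be derived. The documents give neither the sex split nor the share of women of reproductive potential, and they do not record what each woman agreed to at consent. The number affected may be zero. A reader might be tempted to take the number randomized as a measure of the problem. That would be wrong, because it counts men and women together and says nothing about missing undertakings.

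The conclusion rests on the protocol and SAP alone; a consent form containing the undertaking would remove the practical risk, though not the wording error. The timing in the check assumes first dose at randomization. No efficacy or safety analysis changes.

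**What to change.** 1. Send one communication to sites. For each enrolled woman of reproductive potential who is on study drug or within 3 months of stopping, confirm that she has given the bullet 4 undertaking, and obtain it where she has not. This is the step that protects women already in the study. Protocol 15.1.1 does not stand in the way of immediate action for subject safety.

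2. When the protocol is next amended for another reason, change the connector in 8.1 and in the synopsis so that subjects *must meet every one of the following criteria that applies to them*. The content of the bullets stays as it is, and the rule for men does not change. A stand-alone amendment is not worth making. It would need regulatory and IRB/IEC approval across approximately 70 sites, and with enrollment complete and the replacement period over it would reach no new subject.

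The cost is one site communication and renewed consent for any woman without the undertaking. Visits, data collection and analyses do not change.
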